#### 4.2.4 Safety variables

For analyses of AEs and concomitant medication usage, a complete date must be established in order to correctly identify the AE or medication as occurring during treatment or not. If time of study treatment and time of event or concomitant medication is available and non partial then it will also be used however if missing or partial, only the dates will be compared. For purposes of imputing missing components of partially-reported start and stop dates for AEs and for medication use, the algorithms listed below will be followed.

- Missing start day, but month and year present:

If the start of double-blind study medication occurred in the same month and year as the occurrence of the AE/concomitant medication, the start day of the event/concomitant medication will be assigned to the day of first administration of study medication during the double-blind period. Otherwise if informed consent was signed in the same month and year as the occurrence of the AE/concomitant medication, the start day of the event/concomitant medication will be assigned to the day of informed consent.

Otherwise if the following conditions are met:

- the year of the occurrence of the AE/concomitant medication is after the year of the end of the double-blind period or

- the year of the occurrence of the AE/concomitant medication is the same as the year of the end of the double-blind period and the month of the occurrence of the AE/concomitant medication is the after the month of the end of the double-blind period

then the following imputations will be done:

If the year of the occurrence of the AE/concomitant medication is the same as the start of the open-label period and the month of the AE/concomitant medication is the same as the month of the start of the open-label period then the start day of the event/concomitant medication will be assigned to the first day of the open-label period.

Otherwise if the year of the occurrence of the AE/concomitant medication is the same as the start of the SFE period and the month of the AE/concomitant medication is the same as the month of the start of the SFE period then the start day of the event/concomitant medication will be assigned to the first day of the SFE period.

Otherwise the start day will be set to the 1st day of the month.

- Missing start day and month, but year present:

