If the start of double-blind study medication occurred in the same year as the occurrence of the AE/concomitant medication, the start day and month will be assigned to the date of first administration of double-blind study medication. Otherwise if informed consent was signed in the same year as the occurrence of the AE/concomitant medication, the start day and month will be assigned to the day and month of informed consent.

Otherwise if the year of the occurrence of the AE/concomitant medication is after the year of the end of the double-blind period and then the following imputations will be done:

If the year of the occurrence of the AE/concomitant medication is the same as the start of the open-label period then the start day and month of the event/concomitant medication will be assigned to the first day of the open-label period.

Otherwise if the year of the occurrence of the AE/concomitant medication is the same as the start of the SFE period then the start day of the event/concomitant medication will be assigned to the first day of the SFE period.

Otherwise the start day and month will be set to January 1st.

- Missing start day, month, and year:

The start date will be replaced by the date of first study drug administration of double-blind study medication or by the first day of January of the year of the end date, if the first administration date of double-blind study medication is after the end date.

- Missing end day, but month and year present:

The end day will be set to the last day of the month.

- Missing end day and month, but year present:

If the maximum of the subject's date of study termination or the date equivalent to 70 days after the subject's last administration of study medication is the same year as the occurrence of the AE/Concomitant medication, then the end day and month will be set to the maximum

of the date of study termination or the date equivalent to 70 days after last administration of study medication. Otherwise the end day will be set to December 31st of the given year.

- If the stop date is completely unknown, the stop date will not be imputed.

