Any subjects found to be MRI-/CRP- will have their MRI and CRP data examined to see which of the category thresholds they were close to. The subject will still be included in the FAS analyses however they will be assigned into the respective positive category (MRI+/CRP+, MRI+/CRP- or MRI-/CRP+) that they were closest to and documented to have failed inclusion criterion #9. Hence, they will be excluded from per protocol analyses.

Symptom duration will be categorized into  $<5$  and  $\geq 5$  years for subgroup analyses and calculated as:

Start date of symptoms – date of first study medication administration

The start date of symptoms will be found using the medical history of the subject using the following rules (including imputation of partial dates as described in [Section 4.2.4](#)):

- Subjects with a medical history preferred term of ‘Back pain’ or ‘Inflammatory pain’ will use the earliest start date of these symptoms as the start date of symptoms.
- Otherwise, subjects with a preferred term of ‘Axial spondyloarthritis’ will use the earliest start date of disease as the start date of symptoms
- Otherwise, the subject’s medical history will be reviewed in the DEM meeting to determine if the subject has evidence of a start date of symptoms or primary disease.
- Otherwise, the median duration of subjects with a valid symptom duration within the same stratum regarding MRI/CRP classification, will be used as the symptom duration of the subject, unless the duration is  $<3$  months in which case 3 months and 1 day will be used.

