## 6.2 Other Baseline characteristics

In this section, the variables that will be summarized as Baseline characteristic are described.

The different binary items of the ASAS criteria will be presented in frequency tables:

- back pain of ≥ 3 month duration and age of onset < 45 (and per inclusion criteria back pain of ≥ 12 month duration and age of onset < 45)
- active (acute) inflammation on MRI highly suggestive of sacroiliitis associated with SpA
- HLA-B27 positivity (current features)
- inflammatory back pain (history and current features)
- arthritis (history and current features)
- enthesitis (history and current features)
- uveitis (history and current features)
- dactylitis (history and current features)
- psoriasis (history and current features)
- Crohn's disease/ ulcerative colitis (history and current features)
- elevated CRP (history and current features)

Symptom duration (calculated as described in [Section 4.8](#)) and time since diagnosis of disease will be summarized as continuous variables and dichotomized into <5 years and  $\geq 5$  years. Time since diagnosis of disease will be defined as: Earliest start date of the medical history (lower level term) of Axial Spondyloarthritis – date of first study medication administration. If a subject does not have a history of ‘Axial Spondyloarthritis’, then the time since diagnosis of disease will be set equal to the symptom duration.

Frequency tables will be provided for the following Baseline variables related to TB status:

- Contact with an individual with active TB
- Contact with an individual who has recently been treated for TB

Summary statistics will be provided for the laboratory variable CRP. Additionally, CRP at Baseline will be categorized based on the number of subjects with CRP  $\leq$ ULN and  $>$ ULN at Baseline.

Frequency tables will summarize HLA-B27, the test at Screening to rule out hepatitis B surface antigen, and the test at Screening to rule out antibodies to hepatitis C.

Frequencies will also be provided for subjects with the following:

- Peripheral arthritis (swollen joint count  $> 0$ ) at Baseline
- Enthesitis (MASES  $> 0$ )
- Extra-articular manifestations:
  - History of uveitis
  - History of psoriasis
  - History of IBD
- Concomitant DMARDs at Baseline
- Prior DMARDs and prior NSAIDs

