### Date imputation for incomplete or missing start and/or stop dates

Where an AE start date is (partially) missing, the AE will be considered TE if possible.

Imputation rules provided in [Section 4.2.4](#) are based on the assumption that if the start date is incomplete, either day only is missing, or day and months are missing, or date is completely missing.

Although the algorithms for treatment-emergence depend on the onset date, imputation rules are provided for resolution date as well, as these may be needed for certain statistical analyses, such as an analyses of AE prevalence or AE duration.

In order to identify differences between CZP and placebo with respect to TEAEs, the relative risk (CZP/placebo) of the most common TEAEs (incidence >1% for the PT in the CZP treatment group) will be presented graphically by descending relative risk including the 95% CI.

Listings for TEAEs, serious TEAEs, TEAEs leading to withdrawal of study medication, and TEAEs with fatal outcome will be provided. A glossary for the reported terms will also be generated utilizing SOC, HLT, and PT.

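### Section 4.8 dates symptom onset with the adverse-event start-date rules of 4.2.4; read literally, a wholly undated, ongoing symptom record gets a duration of 0 days and bypasses the plan's own fallback

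*SAP*

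**What the plan says.** Section 4.8 derives symptom onset from medical history: "The start date of symptoms will be found using the medical history of the subject using the following rules (including imputation of partial dates". For that imputation it points the reader to section 4.2.4. It then gives four steps:

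1. A subject with a *Back pain* or *Inflammatory pain* term "will use the earliest start date of these symptoms as the start date of symptoms".
2. Failing that, a subject with an *Axial spondyloarthritis* term uses the earliest start of the disease.
3. Failing that, the history is reviewed at the DEM.
4. "Otherwise, the median duration of subjects with a valid symptom duration within the same stratum regarding MRI/CRP classification, will be used", with a minimum of 3 months and 1 day.

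Section 4.2.4 states its own scope: "For purposes of imputing missing components of partially-reported start and stop dates for AEs and for medication use, the algorithms listed below will be followed". Its list nevertheless includes a start with day, month and year all missing: "The start date will be replaced by the date of first study drug administration of double-blind study medication", or 1 January of the end-date year "if the first administration date of double-blind study medication is after the end date". For partial dates, a start in the same year (or same month and year) as first dose is moved to first dose. Otherwise, a start in the same year (or month and year) as informed consent is moved to the consent date.

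The date-imputation text in section 11.2 describes the 4.2.4 rules as covering cases where "either day only is missing, or day and months are missing, or date is completely missing".

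Section 6.2 summarizes symptom duration as a Baseline characteristic, calculated as in 4.8, and refers to "per inclusion criteria back pain of ≥ 12 month duration".

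**The concern.** The 4.2.4 rules lean in one direction by design. When an adverse event's start is unknown, they place it at dosing so that the event counts as treatment-emergent. That is conservative for safety. It is wrong for the onset of a disease that every eligible subject had well before first dose.

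The order of the steps in 4.8 adds to the problem. Steps 1 and 2 are triggered by a preferred term being present, not by its date being known. If a missing date is filled in under 4.2.4, the subject has met step 1 or 2, and steps 3 and 4 are closed.

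Symptom duration (<5 or ≥5 years) is a subgroup for the primary variable (4.8, 8.1.3) and for ASDAS-MI and ASAS40 at Week 156 (8.4). It is also a Baseline characteristic. In 6.2, time since diagnosis is set equal to it when there is no axial spondyloarthritis history. A value of 0 days is not missing, so the exclusion of subjects with a missing category in 4.8 would not catch it.

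**Working it through.** The plan states no figure to reproduce; this is a check of a derivation rule. I assume a first dose of 15 June 2016 for illustration. Duration is taken as first dose minus onset (4.8 prints the difference the other way round, which reverses the sign but not the size). Years are days / 365.25. The closing 1 January step of 4.2.4 is read as the general default for year-only dates.

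**Wholly missing start, 4.2.4 applied literally**

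| End date of record | Imputed onset | Duration | Subgroup |
|---|---|---|---|
| Ongoing | 15 Jun 2016 | 0 days | <5 years |
| 1 Jan 2017 (after first dose) | 15 Jun 2016 | 0 days | <5 years |
| 10 Mar 2016 | 1 Jan 2016 | 166 days = 0.45 years | <5 years |
| 10 Mar 2015 | 1 Jan 2015 | 531 days = 1.45 years | <5 years |
| 10 Mar 2010 | 1 Jan 2010 | 2357 days = 6.45 years | ≥5 years |

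The 0-day result therefore needs three things: no start information at all, a record that is ongoing or ends on or after first dose, and no dated record at the same step, since the earliest start is used.

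**Partial start**

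- Year only, 2005: onset 1 January 2005, 4183 days = 11.5 years, ≥5 years. Nothing collapses to 0.
- Year only, 2016, *Axial spondyloarthritis* record, no back-pain term: moved to first dose, 0 days. Without that step, 1 January 2016 gives 166 days. Both are <5 years, so only the continuous summary changes. There is no dispute over scope here, because the date is partial. The rule puts disease onset on the day of first dose, after the subject was screened for it.
- Year only, in a consent year earlier than the dosing year: moved to consent. Screening lasts at most 6 weeks, so duration is at most 6 × 7 = 42 days. This also stays <5 years.

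**If the fallback were used instead.** A wholly undated onset would go to DEM review and then to the stratum median. The SAP gives no medians, so the resulting subgroup cannot be computed.

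**Number affected.** Not given. Purely as an assumption, 2% to 5% of the 300 planned subjects with wholly undated onset would be 0.02 × 300 = 6 to 0.05 × 300 = 15. The Week 156 figure would be lower, because it counts only subjects who entered the extension, and subjects with another dated record drop out.

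**The case against.** The strongest reply is that 4.8 imports only partial-date imputation, and the introduction to 4.2.4 speaks of partially reported dates. A date with no day, month or year is not partial, so an undated record would go to DEM review and then the median. This reading is reasonable, and it makes 0 days a possible result and not a certain one. It does not close the matter. Section 11.2 counts completely missing dates among those the 4.2.4 rules cover, and steps 1 and 2 of 4.8 do not ask for a usable date. Two programmers could derive different values from the same text.

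The second reply concerns timing. The amendment history shows the wholly-missing rule entering in SAP Amendment 5, for adverse-event dates. Amendment 4 already refers to the Week 52 interim lock analyses. Section 4.3 has all double-blind outputs produced at that lock, and its final-lock list contains no Baseline characteristics table and no double-blind subgroup table. This stands, and it confines the live effect of that rule mainly to the Week 156 subgroups in 8.4. The step moving a dosing-year date to first dose is older, but as shown it cannot change the subgroup.

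Third, sites had to establish at least 12 months of back pain with onset before age 45 to enrol a subject, so a wholly blank onset should be rare. This is plausible and stands as a reason to expect small numbers.

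A reader might infer that long-standing patients in general are set to 0 days and moved to the wrong subgroup. The documents do not support that. A known onset year before the consent and dosing years is kept, an earlier end date moves the imputed onset back, and a dated record at the same step overrides an undated one. Nor does the SAP say that unknown onset is commoner in longer disease.

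**Conclusion.** The point holds as a small specification error. A literal reading of 4.8 with 4.2.4 and 11.2 gives 0 days and the <5-year subgroup for a wholly undated record that is ongoing or ends on or after first dose, when no dated record exists at the same step. That contradicts the back-pain criterion reported in 6.2 and bypasses the two steps 4.8 provides for this situation. A year-only *Axial spondyloarthritis* start in the dosing year is also moved to first dose; this distorts the continuous summary but not the subgroup.

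The consequence is limited to descriptive outputs: mainly the Week 156 symptom-duration subgroups, plus any re-run of Baseline symptom duration, time since diagnosis or the double-blind subgroups. Symptom duration is not in the primary model or in any analysis within the testing hierarchy, so no confirmatory result changes. The size of the effect cannot be stated, because the SAP gives neither the number of undated records nor the stratum medians; the 6 to 15 subjects shown above rest entirely on an assumed 2% to 5%.

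**What to change.** Add two sentences to 4.8:

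- A wholly missing onset date is not imputed under 4.2.4; if the subject has no dated record at steps 1 or 2, the subject passes to DEM review and then the stratum median.
- The 4.2.4 steps that move a partial start date to first dose or to informed consent do not apply to symptom onset.

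Keep the remaining year-only and month-only rules, which work for onset dates. Section 6.2 needs no change, because it takes the derivation from 4.8. A blanket 12-month minimum on imputed durations should not be added, since it could hide an eligibility deviation.

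The cost is two sentences and a change to one derivation. Sample size, the primary analysis and the testing sequence are untouched. Listing the subjects with a wholly undated onset before the final lock would show whether any output changes.

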#### 4.8 Examination of subgroups

Subgroups for age (18 – < 45 years,  $\geq 45$  years), gender (male, female), race (white, other), symptom duration (<5,  $\geq 5$  years), tobacco use (never, current former), HLA-B27 genotype (positive, negative), region (North America, Europe, Asia), prior anti-TNF exposure (yes, no), Baseline SPARCC score (<5,  $\geq 5$  as observed in the 2nd reading session or in the 1st if the 2nd reading is not available), subjects with/without relevant changes to background medication, and MRI/CRP classification (MRI+/CRP+; MRI+/CRP-; MRI-/CRP+) will be utilized for summarizing the primary efficacy variable. Only summary statistics, estimates and confidence intervals will be presented and subjects with missing category will be excluded.

It is possible, that classification errors may occur within the randomization where a subject is found to have been randomized according to the wrong MRI/CRP strata when their MRI data and CRP results are re-examined post randomization. For this reason, the MRI/CRP classification, which will be used in all analyses and subgroup analyses will be one recalculated using the Screening MRI results and second Screening visits CRP results (3 to 5 days prior to Baseline). If the CRP result from the second screening visit is missing, available results from the first screening visit will be used.

Subjects will be categorized as MRI + if they have active (acute) inflammation on MRI highly suggestive of sacroiliitis associated with SpA as determined by the central readers. Otherwise they will be classed as MRI -.

Subjects will be categorized as CRP+ if their second Screening visit CRP result is  $>ULN$ . CRP values  $\leq ULN$  will be considered CRP-. If the CRP result from the second screening visit is missing, available results from the first screening visit will be used. In the unlikely event that a subject has an unavailable recorded CRP result pre Baseline, they will be considered CRP+ for analyses of efficacy but missing for other CRP summaries.

Based on these definitions, the analysis variable for MRI/CRP classification will have the following 3 levels:

- MRI+/CRP+
- MRI+/CRP-
- MRI-/CRP+

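### Symptom onset ignores an older axial spondyloarthritis record, so symptom duration can be shorter than time since diagnosis and a subject can fall on the wrong side of the 5-year subgroup cut

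*SAP*

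**What the plan says.** SAP section 4.8 lists four sources for the start of symptoms, each used only if the one before it is unavailable:

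1. Where the history holds a record coded to either of two pain terms (back pain, inflammatory pain), the subject "will use the earliest start date of these symptoms as the start date of symptoms".
2. Failing that, a subject with the preferred term axial spondyloarthritis "will use the earliest start date of disease as the start date of symptoms".
3. Failing that, the medical history is reviewed at the data evaluation meeting (DEM).
4. Failing that, the median duration in the subject's MRI/CRP stratum is assigned.

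Symptom duration is then split at 5 years. It is a subgroup factor for the primary efficacy variable (sections 4.8 and 8.1.3, where the analyses are repeated for ASAS40 at Week 12) and for the Week 156 ASDAS-MI and ASAS40 summaries (section 8.4).

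Section 6.2 derives time since diagnosis from "Earliest start date of the medical history (lower level term) of Axial Spondyloarthritis". If a subject has no such history, "then the time since diagnosis of disease will be set equal to the symptom duration". Both durations are reported at Baseline as continuous variables and at the 5-year cut.

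**The concern.** Symptoms should start no later than the diagnosis of the disease that causes them. The ladder does not enforce this. Once any pain record exists, the axial spondyloarthritis record drops out of the symptom-onset derivation, however old it is, while section 6.2 goes on using it. Nothing caps symptom onset at disease onset. The DEM review would not catch the case, because it is reached only when neither kind of record exists.

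Two things are at stake. The Baseline table, which describes the trial population, can show subjects diagnosed before their symptoms began. And some of those subjects can be put in the shorter-duration subgroup when their recorded disease is at least 5 years old.

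A lesser matter sits beside it. Where there is no axial spondyloarthritis record, time since diagnosis is filled with symptom duration. Diagnosis normally comes after symptoms, so the fill tends to lengthen the reported time since diagnosis.

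**Working it through.** The SAP gives no count or expected share for these rules, so there is no plan figure to reproduce. The check is to write the rules out and apply them to example dates.

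**Notation.** F = first dose; P = earliest pain record; A = earliest axial spondyloarthritis record. I assume that the same disease record satisfies the searches in both sections.

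**Sign.** Section 4.8 prints the formula as "Start date of symptoms – date of first study medication administration", and section 6.2 subtracts in the same order. Read literally, every duration is negative. I use first dose minus start date throughout.

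**Rules as written**

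- Symptom duration S = F − P if P exists; otherwise S = F − A.
- Time since diagnosis D = F − A if A exists; otherwise D = S.

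**When the order reverses.** With both records present, D − S = (F − A) − (F − P) = P − A. This is positive whenever the disease record is older than the earliest pain record.

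**When the subgroup changes.** The subject moves only if F − P < 5 years and F − A ≥ 5 years.

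**Alternative rule.** S* = F − min(P, A).

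**Examples.** All dates are assumed: first dose 1 July 2016, every record dated 1 July of the year shown, durations in years.

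| Case | Pain record | Disease record | S | D | Subgroup as written | S* and subgroup |
|---|---|---|---|---|---|---|
| A | 2013 | 2009 | 3.0 | 7.0 | <5 | 7.0, ≥5 |
| B | 2009 | 2006 | 7.0 | 10.0 | ≥5 | 10.0, ≥5 |
| C | 2014 | 2013 | 2.0 | 3.0 | <5 | 3.0, <5 |
| D | 2008 | 2014 | 8.0 | 2.0 | ≥5 | 8.0, ≥5 |
| E | 2009 | none | 7.0 | 7.0 (filled) | ≥5 | 7.0, ≥5 |
| F | none | 2010 | 6.0 | 6.0 | ≥5 | 6.0, ≥5 |

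- Cases A, B and C are reversed: D exceeds S by 4.0, 3.0 and 1.0 years.
- Only case A changes subgroup, because only there do the two dates lie on either side of 5 years.
- Case D is in the expected order, and the alternative rule leaves it unchanged.
- In case E the two durations are identical because of the fill in section 6.2. If S is the true symptom duration, the true D is at most 7.0, so the fill can only be too long.
- In case F they are identical because section 4.8 falls back on the disease record.

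**Reach.** Section 4.8 limits the subgroup output to descriptive results with confidence intervals. The primary model in section 8.1.2 contains treatment, region and MRI/CRP classification, not symptom duration. The primary test, its alpha and its power do not depend on these rules.

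**The case against.** The best defence is that the hierarchy is deliberate. A variable called symptom duration should rest on symptom records first, with disease onset as a fallback. That is a reasonable order of preference when records are missing. It does not justify discarding an older disease record that is present, since the result is an ordering that cannot be right for the same disease. Repair also has a cost: the SAP keeps some terminology for consistency with double-blind outputs already produced, so a redefinition now departs from reported tables. That stands and is counted under the fix.

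Several stronger readings are tempting and are not supported:

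- **That the fill in section 6.2 misplaces subjects in the subgroup.** It cannot. The subgroup uses symptom duration alone; the fill applies only without an axial spondyloarthritis history and touches one Baseline summary.
- **That the fill always overstates time since diagnosis.** It tends to. If the symptom duration is itself too short or is a stratum median, it is not a firm upper limit for that subject.
- **That the median rule contradicts section 4.8's statement that "subjects with missing category will be excluded".** The latter is a general rule for all subgroup factors. For symptom duration the SAP has a specific last resort, beginning "Otherwise, the median duration of subjects with a valid symptom duration within the same stratum regarding MRI/CRP classification, will be used as the symptom duration", after which no category is missing.
- **That searching by preferred term in 4.8 and by lower level term in 6.2 changes results.** The terms differ, but whether any record would be classified differently depends on coding that the SAP does not show.
- **That the printed subtraction puts everyone below 5 years.** Literally it would, but section 4.8 also sets a positive floor of just over 3 months for an imputed median, so positive durations are plainly intended.

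**Conclusion.** The point holds in a limited form. Followed as written, sections 4.8 and 6.2 can report symptom duration shorter than time since diagnosis, and can place a subject in the wrong symptom-duration subgroup when the earliest pain record is under 5 years and the disease record at least 5 years before first dose. A reversal alone does not move a subject.

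The number affected cannot be computed from the SAP; it depends on how medical history was recorded and coded. The example shows that the problem is possible, not how common it is. It rests on assumed dates and on the axial spondyloarthritis start date being a valid marker of disease, which is how both sections use it.

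The effect is confined to descriptive tables: Baseline characteristics, the primary-endpoint subgroups (with their ASAS40 Week 12 counterpart) and the Week 156 subgroups. This is a minor correction, worth making because it is cheap and removes an impossible ordering.

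**What to change.** - In section 4.8, define symptom onset as the earliest start date among back pain, inflammatory pain and axial spondyloarthritis records. Keep the DEM review and the stratum median for subjects with none of these.
- In section 6.2, where no axial spondyloarthritis record exists, set time since diagnosis to missing and report n.
- While the text is open, print both durations as first dose minus start date.

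This takes a few lines of SAP text and a small programming change. A few subjects will show a missing time since diagnosis. The Week 52 Baseline and subgroup tables already produced would have to be rerun, or footnoted to say that the definition changed, so that they can be read alongside the Week 156 subgroups. Because treatment codes were to be released to the reporting team at the Week 52 lock (section 4.3), the change should be recorded as made after that lock.
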